3.8 Intervention Design

The KYM-TIFH of this study was formulated and employed by the researchers of this study who work at Pharmaceutical Services Division of Sarawak State Health Department in late 2016 under the national campaign “Know Your Medicine”. It aims to promote medication adherence among T2DM Malay patients due to prevailing nonadherence among them as mentioned earlier. The official name of the intervention is “Kenali Ubat Anda – Ambil demi Kesihatan” in Malay language or “Know Your Medicine – Take it for Health” in English with abbreviation KYM-TIFH. It was specifically designed to complement the individual approach in improving

medication adherence among T2DM Malay patients. This is because group-based intervention can engage more patients at once and serves as building the fundamental capability of patients to adhere with prescribed medications within shorter period as compared to individual approach. Mattson and Hall (2011) advocated that SGBI has numerous irreplaceable benefits that individual approach might not have, including (1) validation; (2) normalization of experience; (3) reduction of isolation; (4) sense of belonging; and (5) enhanced self-esteem. The number of participants for each session of the SGBI is fixed between 20 to 24 participants. The SGBI is only conducted for once with three hours (180 minutes) long and facilitated by one main facilitator and three assistant facilitators. The KYM-TIFH nonetheless had considered the barriers towards medication adherence among T2DM patients (as in Table 1) by incorporating several strategies in designing the program.

3.8.1 Intervention mapping and message design

The KYM-TIFH employed psychosocial, educational and behavioral approach. It was designed based on the application of multiple behavior change theories and persuasion theory as recommended by Slater (1999). The cross-theoretical framework for the message design of intervention as recommended by Slater (1999) involved theories such as Transtheoretical Model (TTM) (Prochaska & Velicer 1997), Theory of Reasoned Action (TRA) (Ajzen & Fishbein 1980), Protection Motivation Theory (PMT) (Rogers 1975), Elaboration-Likelihood Model (ELM) (Petty and Cacioppo 1986) and Social Cognitive Theory (SCT) (Bandura 1992) as in Table 2. Nonetheless, the intervention embrace the philosophy of patients' empowerment, which had found to be effective in engaging patients to produce behavioral change among diabetes patients (Anderson 1995; Anderson et al 1995). Hence, the facilitators are trained to employ non-didactic

approach in facilitating the and eliciting the learning among the group members. The intervention mapping as illustrated in Figure 8, depicts the appropriate outcomes for audiences at each stage of change for use in designing campaign objectives following the recommendations by Slater (1999).

Figure 8: Intervention mapping and the outcomes for audiences at each stage of change

Based on the intervention mapping and message design strategies using cross-theoretical approach, the intervention message delivery strategies are depicted in Table 3. After the completion of the program, participants will be asked to fill in the questionnaire with the assistance of four facilitators (APPENDIX D). A briefing on how to answer the questionnaire will be given by main facilitator and all facilitators are allowed to answer any questions raised by respondents related to the questionnaire. However, they are not allowed to answer on behalf of the respondents. After the completion of the questionnaire, they will be informed about the subsequent follow up measurement after one, three and six month. After that, they will be dismissed and having usual care provided by the health clinic as before without any changes.

Table 2: Message design strategies using cross-theoretical framework approach (adopted from Slater 1999)

Pre-contemplation to contemplation	Contemplation to Preparation	Preparation to action	Action to maintenance
SCT: initiate interpersonal discussion on the issue	TRA: address key beliefs on the issue	SCT: modelling necessary skills to act	TRA: Repeat the behavior
ELM: use credible source to address the issue	SCT: further discussion on the issue	ELM: Use reliable and credible facts to persuade the adoption of behaviour	SCT: See how other people act and set an achievable goal
PMT: increase salience of threat on the issue	ELM: use of anecdote or narrative to address the issue and increase the attitude accessibility	TRA: Reinforce appropriate beliefs and increase the motivation to act	ELM: reinforce the importance of adherence by highly credible sources

SCT: Social Cognitive Theory; ELM: Elaboration-Likelihood Model; PMT: Protection Motivation Theory; TRA: Theory of Reasoned Action.

Table 3: Intervention message delivery strategies

Stage of Change	Message delivery strategies	Times Allocated
Pre-contemplation	
Increase the salience of the issues and maximize message exposure by displaying four standing banners throughout the program, with wordings and pictures that illustrate four different important messages targeting attitude, subjective norm, perceived behavior control and intention towards medication adherence. The message for attitude is “I take as scientific evidences show it does help”; the message for subjective norm is “I take as people important to me want me to take for health”; the message for perceived behavior control is “I take as I make sure I take no matter how”; the message for intention to adhere is “From now on, I will take it for health”.
	Preset
	Answer the questionnaire before intervention begin	15
	
Breaking respondents into 4 groups (5-6 persons/group) and assign group leader of each group before the program begin. Main facilitator welcome the participants and introduce of the other facilitators. Group members introduce themselves to one another by telling their name, their residential area, their
	10 minutes

	favorite food and how long they had been diagnosed with T2DM and how many types of medications they are taking.	
	Present a 5 minutes' video clip on the prevalence of T2DM, disease burden, medication adherence problems among T2DM patients and last with an introduction on the KYM-TIFH and its objective by Deputy Director in Pharmacy Program of Sarawak State Health Department.	5 minutes
	Using role play by facilitators with power point slides to illustrate the pathology of T2DM disease and how does medicines help in managing the disease.	10 minutes
Contemplation	Group members share their attitude and belief on taking medications through writing it down on a mahjong paper with assistance of facilitators. Only key words are written.	10 minutes
	Facilitators will go through the answers given by respondents and recognize the attitude and belief on medication taking behaviors that are correct and rectify those that are incorrect.	20 minutes
Preparation	Present a 5 minutes' video clip that shows an interview of four T2DM Malay patients on their experience in taking medications especially the reasons that they are not adhering the medications as prescribed and how they overcome it.	5 minutes

Group members are asked to write down all their reasons of nonadherence on mahjong paper with 20 minutes assistance of facilitators and think of a way to tackle it through group discussion. Facilitator will present the suggestions given by respondents and share with all participants.

5 minutes' break for participants. At the same time facilitators will distribute the medications belonged to the participants that had been dispensed by outpatient pharmacy department of HCPJ/HCKS.

Action Explain each types of medications for T2DM, how to differentiate the proprietary name and generic name of medicines, storage of medicines and how to read the label using Power Point slides with active engagement with audiences through asking simple questions. 15 minutes

Main facilitator will brief participants on the use of the medication chart (Appendix E) and they will be asked to write down all the medications they have on the chart with the dosage regimen. Subsequently, they need to identify the types of medications which have problem to adhere and discuss with the group on the method they want to take to improve it. 15 minutes

Simulation of taking medications according to the medication chart using their own medications one by one with observation by facilitators to ensure the correctness. The simulation only acquires the participants to show the medicines they are going to take and tell the quantity and timing they need to 20 minutes

	take the medicines to the group facilitator. Facilitators will be able to evaluate the actual understanding and skill in taking medications of participants and rectify right away. Repeat testing the skill of participants until they can demonstrate correct medication taking skill on all their medications.	
Maintenance	Present a 5 minutes' video clip that show the message delivered by (1) Director of Sarawak State Health Department, (2) Deputy Director in Pharmacy Program of Sarawak State Health Department and (3) Dr in charge of Sarawak Traditional and Complementary Medicine Division about the importance of taking medication as prescribed.	5 minutes
	All participants will be taught on how to set goal using SMART strategy (Langford et al 2007) pertaining to their medication adherence and share with their group members.	15 minutes
	Answer the questionnaire after intervention	15
	Total Time	180 minutes

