3.8.2 Content of Control Group

Participants who are assigned to control group, they will be asked to fill in the questionnaire with the assistance of four facilitators (APPENDIX D) right away without any intended input given to participants. A briefing on how to answer the questionnaire will be given by main facilitator and all facilitators are allowed to answer any questions raised by respondents related to the questionnaire. However, they are not allowed to answer on behalf of the respondents. After the completion of the questionnaire, they will be informed about the subsequent follow up measurement after one, three and six month. After that, they will be dismissed and having usual care provided by the health clinic as before without any changes.

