3.8.3 Facilitators and training

To conduct the KYM-TIFH, each session will require one (1) main facilitators and three (3) assistant facilitators to facilitate the program. A total of four (4) main facilitators and twelve (2) assistant facilitators to cater two study sites will be involved in the study. Besides, four qualified and trained facilitators are available for backup. As the number of participants for each sessions of the structured group based intervention is fixed between 20 to 24 participants, each facilitator will assist an average of 5-6 participants.

All the facilitators are the pharmacists who serve under the Pharmaceutical Services Division of Sarawak State Health Department. Facilitators who have experience of conducting at least two times of the intervention will be eligible as the facilitators for this study.

To ensure the consistency and correctness of facilitators in conducting the intervention according to the intervention content, three sessions of the interventions prior to the actual study will be

observed and assessed by the researchers on their performance in terms of coverage of all learning topics, consistency in conducting the intervention, communication with participants and responsiveness to participants' concerns using a structured report namely "Facilitator Competency and Inter-Coder Reliability Assessment Report" (APPENDIX F). All the aspects mentioned above are required to achieve 90%-100% in order to qualified as facilitators for this study. Moreover, among the qualified facilitators, facilitators who were trained to conduct Diabetic MTAC will be appointed as main supervisor. This is because the main facilitators need to have sufficient and up-to-date knowledge in addressing any medication-related-problems raised by participants during the KYM-TIFH. Nonetheless, to ensure the consistency and appropriateness in answering the questions related to the negative perceptions on medication, a booklet of frequently asked questions with answers will be provided to each facilitator and also to participants for their future reference (APPENDIX G).

Apart from training the facilitators to be familiar and consistent in conducting the intervention, the training of the facilitators also includes:

(1) learning how to eliminate concerns and questions the patients come across pertinent to medication adherence with mnemonic tool "ADHERE" adopted from Soto (2004).

- **Acknowledgement:** Acknowledge the concerns of patients.

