3.8.4 Setting of the venue

The setting of the venue for intervention group will be in 4 mini groups. The participants will be asked to count off from one to four in order to break them into the 4 mini groups, only then the intervention will begin. Besides, the four standing banners that aim to enhance the psychosocial variables towards medication adherence will be displayed. The setting of the venue for intervention group is illustrated in Figure 9 while for control group is illustrated in Figure 10.

☺ = Participant; ☹ = main facilitator; 😊 = assistant facilitator; Green rectangle = table

Figure 9: Setting of the venue for intervention group.

☺ = Participant; ☹ = main facilitator; 😊 = assistant facilitator

Figure 10: Setting of the venue for control group

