3.9 Outcome measurement

Primary outcome:

A validated 8-item Malay version of Medication Adherence Scale (MALMAS) will be employed to assess the level of medication adherence among Sarawak patients (Chung et al. 2015). All the items were translated into Bahasa Malaysia and were back translated to English by a group of four experienced language lecturers from University of Malaysia Sarawak.

Secondary outcome:

The psychosocial variables of Theory of Planned Behaviour and adherence information variable from IMB will be employed as secondary outcome of this study. The sources of the items to measure all the variables in conceptual framework are depicted in Table 4.

Paper-based questionnaires will be distributed to the targeted patients by trained enumerators during the group based intervention. Prior to answering the survey, subjects will be briefed about the structure of the questionnaire and how to answer the questions by main facilitator. Any enquiries raised by the respondents will be explained by facilitators.

Table 4: Instrument for the study

Variable	No. of items	Measuring scale	Adopted from
Adherence information	6	5 points Likert scale	McPherson et al. 2008
Attitude to adhere	5	5 points Likert scale	Farmer et al. 2006

Subjective Norm to adhere	6	5 points Likert scale	Farmer et al. 2006
Perceived Behavioural Control to adhere	11	5 points Likert scale	Fernandez et al. 2008
Intention to adhere	3	5 points Likert scale	Vissman et al 2013
Medication adherence	8	1-7 items are measured with binomial answers which are “yes” or “no”; the last item is measured with 5 points Likert scale	Chung et al. 2015
Demographic	15	(1) enrolled with diabetic MTAC; (2) numbers of medications, one or more than one; (3) frequency of the medications, a once-daily dose or more frequent; (4) age; (5) gender; (6) highest education level; (7) monthly household income; (8) employment status; (9) having complications; (10) taking traditional complementary and alternative medicines; (11) residential area, urban or rural; (12) living condition, having social support or stay individually; (13) undergone diabetic education by diabetic nurse; (14) newly diagnosed or established T2DM; (15) concurrent diseases	

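### In the intervention arm only, the facilitators who have just taught the participants also help them complete the post-session psychosocial form, with the programme's banners in view

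*Protocol*

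**What the plan says.** Each intervention session is "facilitated by one main facilitator and three assistant facilitators" (Protocol 3.8). Section 3.8.3 adds: "All the facilitators are the pharmacists who serve under the Pharmaceutical Services Division of Sarawak State Health Department". Staff of that division created the programme (1.3.2, 3.8). Table 3 in 3.8.1 has the facilitators review the attitudes and beliefs that participants have written down, confirm the right ones and put the wrong ones straight.

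Section 3.8.1 then states: "After the completion of the program, participants will be asked to fill in the questionnaire with the assistance of four facilitators". The main facilitator gives a briefing, and "all facilitators are allowed to answer any questions raised by respondents related to the questionnaire". The one limit is: "However, they are not allowed to answer on behalf of the respondents".

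The form is Appendix D, which the legend to Figure 11 identifies as the TPB-IMB scale. Section 3.9 makes those psychosocial variables the secondary outcome, 2.3 builds H3a to H3e on them, and 3.11.4 compares the arms by an independent t test.

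For the intervention venue, 3.8.4 says that "the four standing banners that aim to enhance the psychosocial variables towards medication adherence will be displayed". Table 3 keeps the banners up for the whole programme. They carry one message each on attitude, subjective norm, perceived behavioural control and intention.

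Control participants complete the form "right away without any intended input given to participants" (3.8.2), also with four facilitators, the same briefing, the same permission to answer questions and the same prohibition. Section 3.6 says that participants and facilitators are no longer blinded once the intervention stage is reached.

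**The concern.** The scales ask for the participant's own view of taking medicines. In the intervention arm, the people who explain the items are those who told the participant a short while earlier which views were right. The room also displays the answers that the programme wants on four of the five constructs. A participant may answer to please the teacher, or repeat what was taught, without having changed view. Control participants face no such pressure.

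The t test in 3.11.4 cannot separate this from a true change. Yet Table 5 (3.13) relies on the comparison of the two groups to show that improvement in these variables comes from the intervention. At stake is the interpretation of the five Objective 3 hypotheses, with a likely error in the programme's favour.

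**Working it through.** **1. Are the helpers the same people as the teachers?** The protocol does not say so in one sentence, but the passages allow little else. Section 3.8 gives one main and three assistant facilitators per session, 1 + 3 = 4, and 3.8.1 has four facilitators assisting. Table 3 places the post-session form inside the same 180-minute programme.

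**2. What differs between the arms?**

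| | Intervention (3.8.1, 3.8.4) | Control (3.8.2) |
|---|---|---|
| Four facilitators assist | yes | yes |
| Main facilitator briefs | yes | yes |
| May answer questions on the form | yes | yes |
| May not answer for the respondent | yes | yes |
| Facilitators unblinded (3.6) | yes | yes |
| Helpers have just taught and corrected the respondent | yes | no |
| Banners in view | yes | not described; no intended input |

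Only the last two rows differ. The problem is therefore a demand effect in one arm, and not assistance as such.

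**3. How large could it be?** The protocol gives no figure, so any shift is an assumption. Inputs:

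- Sample sizes from 3.7: 69 per arm, and 221 per arm, which is 170 × 1.3 and so already inflated for dropout. Neither was derived for Objective 3; they serve only as a low and a high reference.
- The 69 reproduces. With difference 1, SD 1.8, power 0.90 and two-sided alpha 0.05 (alpha is not stated there, so it is assumed), n = 2 × (1.960 + 1.282)² × 1.8² / 1² ≈ 68.1, rounded up to 69.
- Assumed one-arm reporting shift b = 0.1, 0.2 or 0.3 SD, with no true effect.

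With z = b / √(2/n), the chance of a two-sided p<0.05 is 1 − Φ(1.96 − z) + Φ(−1.96 − z).

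| b (SD) | z, n = 69 | p<0.05 | z, n = 221 | p<0.05 |
|---|---|---|---|---|
| 0.1 | 0.587 | 9% | 1.051 | 18% |
| 0.2 | 1.175 | 22% | 2.102 | 56% |
| 0.3 | 1.762 | 42% | 3.154 | 88% |

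The nominal rate is 5%. The rate rises with n because a larger sample detects the bias more surely and does nothing to reduce it.

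**4. How much would the fix remove?** This is unknown too. If it halved an assumed 0.2 SD shift, the rate at 221 per arm would fall from 56% to 18%, which is still above 5%.

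**The case against.** The strongest reply is that the form is self-completed, so the facilitators score nothing, and that both arms get the same help under the same rules from unblinded staff. That is correct. It rules out describing this as assessor bias confined to one arm. It leaves the difference in prior contact, which the ban on answering for respondents does not address.

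Second, much of any demand effect comes with an immediate self-report after an educational session that cannot be blinded, whoever is in the room. This stands. The percentages above describe a whole assumed shift, not the gain from changing staff.

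Third, Table 3 puts the banners up before the pre-session form, so the baseline also appears to be completed in their view. An effect of the banners on answers would then partly cancel in a before-after change. This stands for the banners. It does not cover the teaching and correction, which fall between the two forms, nor a comparison of post-session values, which is how H3a to H3e are worded.

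Fourth, a reader might infer that 3.8.1 and 3.9 contradict each other on who handles the form, since 3.9 says: "Paper-based questionnaires will be distributed to the targeted patients by trained enumerators during the group based intervention". They do not. Section 3.9 goes on to give the briefing to the main facilitator and the answering of enquiries to the facilitators, which agrees with 3.8.1. Nor does it say that the enumerators are separate people, so they cannot be counted on as independent helpers.

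**Conclusion.** The point holds for the post-session psychosocial form. An avoidable demand or courtesy effect, specific to the intervention arm, is mixed into the between-group comparison for H3a to H3e. Its direction probably favours the programme and its size is unknown. The illustrative range is a 9% to 88% chance of p<0.05 with no true effect, for assumed shifts of 0.1 to 0.3 SD and 69 to 221 per arm.

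This rests on the shift being as assumed, and on the same-day form serving for Objective 3. The schedule in Figure 11 is not shown, so it cannot be confirmed that this form is the only time point used.

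A reader might extend the point to the primary outcome, the MALMAS adherence score. The document does not support that. Table 4 lists the scale among the instruments, but the protocol does not say who administers the forms at one, three and six months, so bias in that follow-up is not demonstrated.

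**What to change.** Amend 3.8.1, 3.8.2 and 3.9 as follows.

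- The team that delivered a session does not brief or assist its own participants on the form.
- Named non-delivering staff do this instead: the other venue's team or the trained backups. Section 3.8.3 lists four main facilitators, twelve assistants (the bracketed figure there reads 2, but three per main facilitator gives 12) and four backups. Section 3.6 gives each site two venues.
- One scripted briefing, with scripted replies to common questions, is used in both arms.
- Pre-session and post-session forms are completed with the banners out of view, by covering them or using another room.
- The same rule may be stated for the one-, three- and six-month forms. There it is preventive only.

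The content of the programme does not change. The cost is rostering, a short changeover at the end of each session and some waiting. Control participants leave after one form while the programme lasts 180 minutes, so a control-venue team would have to wait or return, and the protocol does not say that the two venues run at the same time. The substitutes would still be unblinded pharmacists of the same division, so the report should still say that some demand effect may remain in these outcomes.

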2.3 Hypotheses

Based on the first specific objective, two hypotheses to be tested are:

H1a: There is significant difference of medication adherence level among participants before and after the intervention.

H1b: There is significant difference of medication adherence level after the intervention between participants from intervention group and control group.

Based on the second specific objective, six hypotheses to be tested are:

H2a: There is a significant relationship between attitude to adherence and intention to adhere.

H2b: There is a significant relationship between subjective norm to adherence and intention to adhere.

H2c: There is a significant relationship between perceived behavior control to adherence and intention to adhere.

H2d: There is a significant relationship between perceived behavior control to adherence and medication adherence.

H2e: There is a significant relationship between intention to adherence and medication adherence.

H2f: There is a moderating effect by adherence information between intention to adhere and medication adherence.

Based on the third specific objective, five hypotheses to be tested are:

H3a: There is significant difference of attitude to adhere after the intervention between participants from intervention group and control group.

H3b: There is significant difference of subjective norm to adhere after the intervention between participants from intervention group and control group.

H3c: There is significant difference of perceived behavioural control to adhere after the intervention between participants from intervention group and control group.

H3d: There is significant difference of intention to adhere after the intervention between participants from intervention group and control group.

H3e: There is significant difference of adherence information after the intervention between participants from intervention group and control group.

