3.11.4 Data analysis for third objective

The third objective is to measure the impact of the intervention on psychosocial variables among participants. The change of the psychosocial variables before and after the intervention within the groups will be tested using paired t test. While the change of psychosocial variables before and after the intervention between the groups will be tested using independent t test.

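### Nothing in the text keeps the four intervention banners out of view while the intervention arm answers its pre-session questionnaire, so its psychosocial 'before' scores are probably taken under exposure

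*Protocol*

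**What the plan says.** Table 3 in section 3.8.1 lists the message delivery steps in order. The first row, under pre-contemplation, is the banner display, meant to "maximize message exposure by displaying four standing banners throughout the program". Its time entry is 'Preset', and the banners carry "four different important messages targeting attitude, subjective norm, perceived behavior control and intention towards medication adherence". The second row, given 15 minutes, reads "Answer the questionnaire before intervention begin". Forming the small groups comes third.

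Section 3.8.4, describing the intervention venue, says that "the four standing banners that aim to enhance the psychosocial variables towards medication adherence will be displayed". The text mentions no banners for the control venue. Section 3.8.2 has controls fill in the questionnaire "right away without any intended input given to participants".

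Section 3.11.4 uses the scores in two ways. Within groups: "The change of the psychosocial variables before and after the intervention within the groups will be tested using paired t test". Between groups: "While the change of psychosocial variables before and after the intervention between the groups will be tested using independent t test".

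Section 2.3 words the hypotheses differently. H3a reads "There is significant difference of attitude to adhere after the intervention between participants from intervention group and control group", and H3b to H3d follow the same pattern for the other three constructs.

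**The concern.** A 'before' score should be taken before any treatment component reaches the participant. Here the component listed first is a set of first-person slogans, one per construct, which the protocol itself says are meant to raise those constructs. If they hang in the room while the form is answered, the intervention arm's starting point is measured under part of the treatment and the control arm's first form is not.

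The difference arises after randomisation, so randomisation does not balance it. If the banners work as intended, they lift the intervention arm's 'before' scores and shrink its before-after change. A table comparing the arms on those scores could also show an imbalance created by the setting rather than by chance. Once the sessions have been held, a clean pre-session score cannot be recovered.

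**Working it through.** The point turns on the order of procedures. The protocol gives no figure to reproduce.

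**1. Is the form answered with the banners on view?**
- Table 3 puts the banners in place first and the form second.
- Section 3.9 says the paper questionnaires are handed out in the group session.
- Nothing in sections 3.8.1, 3.8.4 or 3.9 covers the banners or moves the form to another room.

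Exposure is the natural reading, but it is an inference from the 'Preset' entry and the row order.

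**2. Does the stated session length settle it?** The Table 3 minutes, in order and with the 5-minute break, are
15 + 10 + 5 + 10 + 10 + 20 + 5 + 20 + 5 + 15 + 15 + 20 + 5 + 15 + 15 = 185.
Without the break: 185 − 5 = 180, the stated total. Leaving out the pre-session form gives 185 − 15 = 170 with the break, or 180 − 15 = 165 without it. So 180 is reached only if the form is counted. But the same total also counts the 15-minute closing questionnaire, which section 3.8.1 places after the programme has finished. Being counted in the 180 minutes therefore does not prove that the form falls within the banner display.

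**3. Is there another psychosocial baseline?** Section 3.5 names only MALMAS for the June screening. The text describes no earlier administration of the psychosocial scales. Figure 11, the timeline, is not shown, so an earlier measurement there cannot be excluded.

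**4. Which analyses are affected?** For one construct, write:
- m for the unexposed mean;
- D for the intervention arm's true change;
- B for the lift already produced by the banners when the 'before' form is answered (B ≥ 0 if they work as intended);
- c for the control arm's change.

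The closing score is the same with or without early exposure, because the banners are on display later in any case.

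| Analysis | Clean 'before' | Exposed 'before' |
|---|---|---|
| Within intervention arm, paired t test | (m + D) − m = D | (m + D) − (m + B) = D − B |
| Between arms, change | D − c | D − B − c |
| Between arms, 'after' scores only | (m + D) − (m + c) = D − c | D − c |

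The two change analyses lose B. The post-only comparison loses nothing. With b = B/D, the within-arm change shrinks by the factor (1 − b). The documents give no value for b, and any value put in would simply return itself as the percentage lost.

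**5. Which outcomes are affected?** The scales behind H3a to H3d are affected. Adherence information (H3e) has no banner. MALMAS is taken at the June screening, before any session, and again at follow-up, so the argument does not reach the primary outcome.

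**The case against.** The strongest reply is that the protocol never says the form is answered in front of the banners. Its own wording suggests the form comes before the programme: the group-forming row in Table 3 is described as preceding the start, and section 3.8.4 says the intervention begins only after the count-off. Figures 9 and 10, which show the two venues, are not available. This stands as a limit on certainty. It does not remove the problem, because calling the form pre-intervention does not take down banners already listed as in place.

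A reader might go further and infer that the tests of H3a to H3d are biased. The documents do not support that. Section 2.3 words these hypotheses as differences after the intervention, and an exposed 'before' score does not enter such a comparison. Only the change analyses in section 3.11.4 are open to it.

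Even there, the between-arm test is not fully defined. Section 3.8.2 describes a single same-day form for controls, so the text does not supply a control pair that matches the intervention arm's two in-session forms. The between-arm consequence therefore holds only where a 'before' score is actually used.

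Finally, the exposure is passive and lasts roughly the 15 minutes allotted to the form, within a three-hour facilitated session. The outcomes are secondary and the likely error is conservative. All of that is fair and bears on size and priority.

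**Conclusion.** The point holds within limits. As written, the intervention arm's 'before' scores for attitude, subjective norm, perceived behavioural control and intention are probably taken with treatment messages in view, while controls receive no intended input. The likely effect is to understate the intervention arm's change in the paired test and, where a 'before' score is used, in the between-arm test of change.

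This rests on two assumptions: that the banners are visible while the form is answered, and that they move the scores in the intended direction. The size is unknown and may be small. It would be wrong to attach a percentage or a loss of power to it from these documents. It would also be wrong to treat the 180-minute total as proof of exposure, or to extend the point to post-intervention comparisons, H3e or MALMAS. It is worth correcting because the remedy costs almost nothing and the baseline cannot be retaken.

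**What to change.** State in Table 3 and in section 3.8.4 that the four banners stay covered, or are not put up, until all pre-session questionnaires in the intervention venue have been collected. Move the banner row in Table 3 below the questionnaire row to match. Reordering the rows without that statement would not change what participants see.

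The cost is about a minute of set-up per session, with the same forms, staff and timetable.

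Having the form completed at registration, before participants learn their venue, would also work but is not free. The form needs a briefing and help from facilitators (sections 3.8.1 and 3.8.2), whereas registration is run by the independent society (section 3.6). Covering the banners is the simpler choice.
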